#### **15.6.3. Exploratory Objectives #6: Radionecrosis**

Rates of radionecrosis will also be determined based on radiographic and clinical suspicion or tissue confirmation when available. The proportion of patients who experience radionecrosis will be estimated with confidence intervals in the two treatment groups.

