Importantly, **no patients in the neoadjuvant group experienced surgical delay**, suggesting that administration of checkpoint inhibitors prior to surgical resection is safe.

Given that immunotherapy, specifically nivolumab and ipilimumab, have been shown to have significant anti-tumor activity in brain oligometastases [12], and that administration of checkpoint inhibitors prior to surgery results in improved overall survival in patients with GBM [16], investigating the timing of immunotherapy administration in patients with brain metastases is clinically important. Towards this end, we have designed a single-arm clinical trial of neoadjuvant nivolumab and ipilimumab in patients with asymptomatic or minimally symptomatic brain metastases known to have spread from primary tumors that are traditionally responsive to immunotherapies. The percentage of patients experiencing surgical delay in the neoadjuvant treatment arm will be recorded to assess feasibility. Immunotherapy activity will be established by assessing the change in T-cell proliferation levels in circulation between baseline and Day 1 (see Section 12.7.5).

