## 8. OBJECTIVES AND ENDPOINTS

	Objective	Endpoint	Analysis
Primary	Assess the feasibility of neoadjuvant ipilimumab and nivolumab treatment before surgery and SRS among patients with solid tumor brain metastases	Among eligible patients, the percentage of patients who experience surgical delay. Surgery is considered delayed if it occurs more than 10 days after ipilimumab and nivolumab, or never occurs, for reasons relating to the immunotherapy treatment.	See Section 15.5.1
Other Primary	Demonstrate that neoadjuvant immunotherapy will increase proliferation of circulating T-cells compared to baseline measurements	Mean fold-change between baseline and day 1 in Ki67 levels	See Section 15.5.2
Exploratory	Describe the survival of patients with solid tumor brain metastases receiving neoadjuvant ipilimumab and nivolumab followed by surgery and SRS.	Median survival	See Section 15.6.1
Exploratory	Describe the time to local intracranial progression	Median time to local intracranial progression	See Section 15.6.2
Exploratory	Describe the time to distant intracranial progression	Median time to distant intracranial progression	See Section 15.6.2
Exploratory	Describe the time to overall intracranial progression (local or distant)	Median time to overall intracranial progression (local or distant)	See Section 15.6.2
Exploratory	Describe progression-free survival	Median progression-free survival	See Section 15.6.2
Exploratory	Quantify the rate of radiation necrosis	Percent of patients with radiation necrosis	See Section 15.6.3
Exploratory	Describe immune express profiles	Normalized immune expression	See Section 15.6.4

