### **9.1.7. Randomization**

As of 03/19/2021, randomization was removed from the study when a control arm without neoadjuvant nivolumab and ipilimumab was removed from the study design. See details in Section 15.1.

[figure not shown]

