### 15.1. Study Design Overview

This randomized phase II trial is conducted among patients with surgically-resectable, solid tumor brain metastases to assess the impact of neoadjuvant nivolumab and ipilimumab administered before surgery and stereotactic radiosurgery on various clinical and biological endpoints.

The study was originally designed as a randomized phase 2 trial in which patients were randomized via a permuted block randomization algorithm using a 1:1 allocation ratio to receive either Arm 1 (with neoadjuvant nivolumab and ipilimumab) or Arm 2 (without neoadjuvant treatment). Unfortunately, the study faced challenges to enrollment due to delays in treatment caused by the randomizing of patients to a control arm. In a Memo to File dated March 4, 2021 that was submitted to the IRB and FDA, we proposed the removal of randomization in favor of a single-arm study in which all patients will receive neoadjuvant immunotherapy prior to their resection and SRS. This change is reflected in the protocol's amendment date 03/19/2021. This change will not affect the primary endpoint of feasibility. Prior to the writing of this Memo to File, 1 patient had been randomized to receive standard of care surgery and SRS without neoadjuvant immunotherapy. This patient, though eligible, will not be part of the analyses described below.

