### **15.6.2. Exploratory Objectives #2 - #5: Disease Progression**

Several different efficacy measures of progression will be computed as part of exploratory objectives #2 - #5:

- The time to local intracranial progression is the time between initiation of checkpoint treatment and first identification of local intracranial progression, which is defined by RANO-BM criteria. If a patient experiences a distant intracranial progression or dies before documentation of local progression, the time to local intracranial progression will be censored at the time of distant intracranial progression or the time of death.
- The time to distant intracranial progression is the time between initiation of checkpoint treatment and first identification of distant intracranial progression, which is defined by RANO-BM disease progression criteria. If a patient locally progresses intracranially or dies before documentation of distant intracranial progression, the time to distant intracranial progression will be censored at the time of local intracranial progression or the time of death.
- The time to overall intracranial progression is the time between initiation of checkpoint treatment and first identification of intracranial progression (distant or local), as defined by RANO-BM criteria. If a patient dies before documentation of intracranial progression, the time to overall intracranial progression will be censored at the time of death.

- Progression-free survival is the time between initiation of checkpoint treatment and first progression (intracranial or extracranial), or death if the patient dies without documented disease progression, as defined by RECIST 1.1. If the patient remains alive without disease progression at the time of analysis, progression-free survival will be censored at the time of last follow-up.

Given that death, local intracranial recurrence, and distant intracranial recurrence are competing events, time to local intracranial recurrence, time to distant intracranial recurrence, and time to overall intracranial recurrence will be graphically described using a cumulative incidence function.

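### Section 15.6.3 plans radionecrosis as a crude proportion in two groups of a single-arm trial, with no at-risk set, time origin or rule for incomplete follow-up, so the rate can be diluted

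*Combined protocol and SAP*

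**What the plan says.** The endpoint table in Section 8 lists the measure as "Percent of patients with radiation necrosis". Section 15.6.3 takes cases on "radiographic and clinical suspicion or tissue confirmation when available" and then states: "The proportion of patients who experience radionecrosis will be estimated with confidence intervals in the two treatment groups". Neither place gives a denominator, a start of follow-up, a time point or an interval method.

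Section 15.2 assigns an analysis set to feasibility, survival, progression-free survival and time to intracranial progression. Radionecrosis is not on that list.

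On the design, Section 9.1.7 records that "randomization was removed from the study when a control arm without neoadjuvant nivolumab and ipilimumab was removed from the study design", Section 7.3 says "we have designed a single-arm clinical trial of neoadjuvant nivolumab and ipilimumab", and Section 15.1 says of the one patient already randomized to control: "This patient, though eligible, will not be part of the analyses described below".

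For the intracranial progression endpoints, Section 15.6.2 chooses a cumulative incidence function, with the reason "Given that death, local intracranial recurrence, and distant intracranial recurrence are competing events". That method is not carried over to radionecrosis.

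**The concern.** There are two separate problems.

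- **The wording cannot be followed.** There is no second group to report.
- **The quantity is not defined.** Radiation necrosis can arise only in patients who were irradiated. The plan itself foresees patients who do not get that far: the CONSORT diagram in Section 15.4 counts surgery that is late or never happens, and counts who receives SRS. It also foresees incomplete observation. Section 12.5 has a status code for patients lost to follow-up, and Section 12.6.2 asks for contact with withdrawn patients only where possible and does not require imaging. Adverse event collection stops 100 days after surgery (Section 13.1), so later cases depend on brain MRI and clinic visits.

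A simple proportion can only count a partly observed patient as event-free or drop that patient. With the rule left open, the choice could be made after the data are seen. At stake is how a named exploratory objective is read: the rate of radiation necrosis when checkpoint inhibitors are given before SRS.

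**Working it through.** **No figure to reproduce.** The plan states no expected radionecrosis rate, precision target or sample size for this endpoint. What follows is illustration. From the documents: up to 20 treated patients (Sections 5.3 and 9.1), 18 months of follow-up from study treatment (Section 9.1), SRS about 4 weeks after dosing (7 days plus 3 weeks, Section 9.1), and a background median survival of about 10.8 months (Section 7.1). Assumed: the necrosis rate, the share without SRS and the loss rate.

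**1. Number of groups.** Sections 7.3, 9.1.7 and 15.1 leave one arm, and the single control patient is outside the analyses. The number of reportable groups is one.

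**2. Denominator.** If k of 20 patients have no SRS and all 20 are counted, the crude rate is the rate among SRS patients times (20 - k)/20. For k = 1, 2, 3, 4 the factor is 0.95, 0.90, 0.85, 0.80, so each patient costs a relative 5%. With 3 cases (exact Clopper-Pearson intervals):

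| Denominator | Estimate | 95% CI |
|---|---|---|
| 20 (all treated) | 15.0% | 3.2-37.9% |
| 18 (2 without SRS) | 16.7% | 3.6-41.4% |
| 17 (3 without SRS) | 17.6% | 3.8-43.4% |

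**3. Adding loss to follow-up.** Constant hazards per month: death m = ln 2/10.8 = 0.0642; necrosis h = 0.02 (assumed); loss l = 0, 0.01 or 0.02 (assumed). Time at risk after SRS: T = 17 months.

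Probability of observed necrosis = h/(h+m+l) × (1 - exp(-(h+m+l)T))

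- l = 0: 0.2376 × 0.7610 = 18.1%, the true cumulative incidence after SRS
- l = 0.01: 0.2124 × 0.7983 = 17.0%
- l = 0.02: 0.1920 × 0.8298 = 15.9%

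Multiplying by 0.90 or 0.80 for patients without SRS gives the crude proportion, with the relative shortfall from 18.1% in brackets:

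| Monthly loss | 10% without SRS | 20% without SRS |
|---|---|---|
| 0% | 16.3% (10%) | 14.5% (20%) |
| 1% | 15.3% (16%) | 13.6% (25%) |
| 2% | 14.3% (21%) | 12.7% (30%) |

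In absolute terms the shortfall is 1.8 to 5.4 points.

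**4. Second model as a check.** Take a 15% necrosis risk over 17 months, ignore death, and spread losses evenly over the period. A lost patient's mean risk while observed is then 1 - 0.15/0.1625 = 7.7%. With 2/20 lacking SRS and 20% lost: 0.90 × (0.8 × 15% + 0.2 × 7.7%) = 12.2%. With 3/20 and 30%: 0.85 × (0.7 × 15% + 0.3 × 7.7%) = 10.9%, a factor of 0.73. The size is similar.

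**5. Death.** With l = 0 and everyone given SRS, the crude proportion in step 3 is 18.1%, the same as the cumulative incidence with death competing. A 15% risk in the absence of death corresponds to a cumulative incidence of about 9% at a 10.8-month median survival, but that is a different quantity, not an error in the proportion.

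**6. Usable time points.** Eighteen months from dosing less about 4 weeks leaves about 17 months after SRS. Six and 12 months lie inside this window; 18 months after SRS does not.

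**The case against.** The best defence is that the text is silent rather than wrong. Section 15.6.3 does not say that all treated patients are the denominator or that lost patients count as event-free, and Section 15.2 does not settle it. A reader might infer that the reported rate is bound to be understated. The documents do not support that; they support only that it would be if those patients were counted that way.

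Other points on that side stand:

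- Eligibility requires planned resection and post-surgical SRS (Section 11.1), and follow-up is a fixed 18 months per patient. Missed SRS and loss may both be rare, and no rates are given.
- Cases may be counted on suspicion, and false positives would push the rate up. A reader might infer that the plan makes the treatment sequence look safer than it is, but the net direction is not settled.
- A proportion over everyone who starts the sequence is a legitimate quantity if it is declared, and the CONSORT diagram will show how many had SRS.
- A reader might take the two-group sentence as a lost comparison. It plans only an estimate in each group, so removing it is an editorial correction.
- The endpoint is exploratory, and no threshold or stopping rule depends on it.

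This lowers the weight of the point but does not answer it. An undefined denominator and no rule for partial follow-up remain, although the same plan already uses a suitable method for its progression endpoints.

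**Conclusion.** The point holds in a limited form. The two-group wording contradicts the single-arm design, whatever is assumed. The analysis lacks an at-risk set, a time origin and a rule for incomplete follow-up.

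The resulting dilution is conditional. It is a relative 5% per patient without SRS among 20, and about 10-30% with an assumed 10-20% lacking SRS and 0-2% monthly loss. It is zero if all receive SRS and none is lost. Even the largest shift shown, 5.4 points, is about the weight of one patient in 20 (5 points) and is small against an interval of 3.2-37.9% for 3/20.

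A reader might also infer that early deaths bias the crude proportion. With complete follow-up they do not, because it then equals the cumulative incidence with death competing. The reason to change the method is the handling of non-irradiated and partly observed patients. The primary objectives are not affected.

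**What to change.** In Section 15.6.3:

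- Delete the reference to two groups.
- Define the analysis set as patients who start SRS, and add radionecrosis to Section 15.2.
- Count time from SRS.
- Estimate the cumulative incidence of radionecrosis with death as a competing event, as in Section 15.6.2. Censor patients alive without radionecrosis at their last brain assessment.
- Report estimates with 95% CIs, naming the interval method, at time points inside the observed window, for example 6 and 12 months after SRS. Do not promise an 18-month estimate from SRS.
- Align the endpoint entry in Section 8.

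The cost is a few sentences and one more use of a method already planned. No new data collection is needed. The downside is slightly more analysis work and a slightly wider interval from the smaller denominator.

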#### **15.6.4. Exploratory Objectives #7: Immune Expression Profiles**

Various exploratory analyses will be conducted to describe the immune expression profiles of patients. As noted previously immune profile assays may be run on cells from peripheral blood, resected tissue, and archival tissue using RNASeq, 28 color flow cytometry, IHC, and other methods. Some analyses may not be pre-specified, and may be motivated by other study findings or the evolving clinical literature that is available at the time accrual has been completed.

Nanostring expression data will be normalized as per system guidelines. Exploratory analysis of highly differentially expressed genes will be utilized in assessing association to Ki67 from circulating PD-1/CD8+ T cells and to intratumoral PD- 1/CD8+ T cells. Additionally, differentially expressed genes will be incorporated in exploratory models of survival outcomes.

### **15.7. Interim Analysis**

No interim efficacy analyses will be performed. However, continuous monitoring of surgical timing/delay will occur as described in Section [15.5.1.2](#).

## **15.8. Sample Size Calculation**

Twenty (2) patients will be enrolled onto this study and treated with ipilimumab and nivolumab. We anticipate that due to drop-out and/or sample quality issues Ki67 data will be available from approximately 17 patients.

Kim et al (2019) [23] reports that a higher fold-change in the percentage of Ki-67+ cells among PD1+ CD8+ T cells 7 days after the first dose of anti-PD-1 therapy is associated with greater efficacy. The distribution of this fold-change is graphically presented in Figure 2A of the Kim article. Based upon a crude estimate of the value of Ki-67 associated with each data point in this figure, mean fold-changes were computed. The mean fold- change among the 11 patients with durable clinical response is 4.9 (SD=2.0; CV = 0.42); whereas the mean fold-change among the 20 patients with non-durable response is 2.5 (SD=1.3; CV=0.54). Overall, the mean fold-change is 3.4 (SD=2.0; CV=0.6).

Assuming that CV=0.6, a one-sample t-test ( $\alpha=0.05$ ; two-tailed) has >95% power to detect a mean fold- change of 1.7 among the 17 patients with evaluable Ki67 data.

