### **5.6. Data Analysis and Statistical Considerations**

Feasibility will be assessed by the proportion of patients who have their surgery delayed. With the checkpoint inhibitors being administered on Day -7, the surgery is scheduled for Week 1, Day 1 ( $\pm$  3 days). *Surgery will be considered delayed if it never occurs or occurs after Day 4 (i.e. Day 1 + 3).* The proportion of patients experiencing surgical delay as defined in Section 15.5.1.1 will be computed as the number of patients with delay divided by the total number of patients per arm. Methods developed for continuous monitoring of toxicity will assess whether the number of surgical delays is excessive. Monitoring rules based upon Pocock monitoring rules are provided in Section 15.5.1.2.

A one-sample t-test will assess whether significant changes fold-change in Ki67 levels between baseline and Day 1 occurred.

Kaplan-Meier methodology will be used to graphically display survival and progression-free survival; whereas, cumulative incidence curves will be used to graphically display time to local intracranial progression, time to distant intracranial progression, and time to overall intracranial progression as defined in Section [15.6.2](#).

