### **15.5.2. Primary Objective #2: Proliferation of Circulating T-Cells**

The second primary objective involves an assessment of whether neoadjuvant immunotherapy will increase proliferation of circulating T-cells compared to baseline measurements.

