#### **15.5.2.2. Statistical Hypothesis, Model, and Method of Analysis**

As noted in Section [15.5.2.1](#), the primary outcome for each patient is the fold- change in Ki67 levels between baseline and Day 1. The mean fold- change will be tested using a one-sample t-test. If assumptions for conducting a t-test are violated, a logarithmic transformation may be considered as well as a Wilcoxon one-sample test.

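### The >95% power stated in 15.8 does not hold for the planned raw-scale t-test at a mean Ki67 fold-change of 1.7; it is about 76–88%, and the null and the meaning of 1.7 are not written

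*Combined protocol and SAP*

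**What the plan says.** The second primary objective asks whether "neoadjuvant immunotherapy will increase proliferation of circulating T-cells compared to baseline measurements" (Section 15.5.2). Section 8 gives the endpoint as "Mean fold-change between baseline and day 1 in Ki67 levels". Section 15.5.2.2 specifies the analysis: "The mean fold- change will be tested using a one-sample t-test". If the assumptions of the t-test fail, "a logarithmic transformation may be considered as well as a Wilcoxon one-sample test". The synopsis (5.6) also names only the one-sample t-test: "A one-sample t-test will assess whether significant changes fold-change in Ki67 levels between baseline and Day 1 occurred".

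Section 15.8 takes its variability from a published figure, read off by eye. For the non-durable group, "the mean fold-change among the 20 patients with non-durable response is 2.5 (SD=1.3; CV=0.54"); for all patients, "Overall, the mean fold-change is 3.4 (SD=2.0; CV=0.6"). The durable-response group has mean 4.9, SD 2.0 and CV 0.42. These are all summaries of untransformed ratios. Taking a CV of 0.6, two-sided alpha 0.05 and 17 evaluable patients, it then claims ">95% power to detect a mean fold- change of 1.7 among the 17 patients with evaluable Ki67 data".

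The plan does not state the null value of the test, whether 1.7 is an arithmetic or a geometric mean, or whether the power was calculated on the log scale.

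**The concern.** A reader who takes 15.8 together with Sections 8 and 15.5.2.2 will understand 1.7 as an arithmetic mean, tested on the raw scale against no change. On that reading the effect is 0.7 and the SD is 1.02, a standardised effect of about 0.69. With 17 patients that is too small for 95% power.

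This is one of two primary objectives and the only one with a stated power. If the figure is wrong for the planned test, the plan misstates the effect it can reliably detect. There is a second consequence. The choice between raw and log scale is left open, with no stated trigger, so the quantity being estimated could move between an arithmetic and a geometric mean after the data are seen.

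**Working it through.** **Inputs.** From 15.8: mean fold-change 1.7, CV 0.6, n = 17, two-sided alpha 0.05. From 15.5.2.2: one-sample t-test on the untransformed mean. Assumed, because no section gives it: null fold-change = 1, the value for no change from baseline.

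**Formula.** The standardised effect is d = (mean − null)/SD, and the noncentrality is d√n. Power is the probability that a noncentral t with 16 degrees of freedom exceeds 2.120 in absolute value.

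**Reproducing the stated figure.** It can be matched on the log scale:

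- Log-scale SD for log-normal ratios: σ = √ln(1 + 0.6²) = 0.5545.
- Treating 1.7 as a geometric mean: d = ln(1.7)/0.5545 = 0.957; noncentrality = 0.957 × √17 = 3.95; power = **95.9%**.
- The smallest geometric mean giving 95% is about 1.68, which rounds to 1.7. This is probably how the figure was obtained.

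**The planned raw-scale test at an arithmetic mean of 1.7.**

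- SD = 0.6 × 1.7 = 1.02; d = 0.7/1.02 = 0.686; noncentrality = 2.83; power = **75.7%** (normal data).
- Simulating the same test with 400,000 trials per case: about **83%** for gamma ratios and about **88%** for log-normal ratios.

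**Sensitivity to the CV (normal data, mean 1.7).**

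| CV | Source in 15.8 | Power |
|---|---|---|
| 0.42 | durable response | 96.6% |
| 0.54 | non-durable response | 83.9% |
| 0.60 | overall, the value assumed | 75.7% |

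Reaching 95% needs a CV of no more than 0.44.

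**Mean detectable with 95% power (raw test, CV 0.6, n = 17).** About 2.27 (normal), 1.93 (gamma) or 1.83 (log-normal).

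**Power at the published means (raw test, normal data, CV 0.6).** At 2.5, d = 1.5/1.5 = 1.0 and power is 97.2%. At 3.4, d = 2.4/2.04 = 1.18 and power is 99.5%.

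**Other readings that exceed 95%.**

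- Raw test on log-normal data with a *geometric* mean of 1.7: 98.3%. Under log-normality the arithmetic mean is then 1.7 × exp(σ²/2) = 1.98, not 1.7.
- SD fixed at 0.6: d = 0.7/0.6 = 1.167 and power is about 99.5%. The CV at 1.7 is then 0.6/1.7 = 0.35, which contradicts the stated 0.6.

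**The log-scale test at an arithmetic mean of 1.7.** The geometric mean is 1.7/exp(σ²/2) = 1.458, so d = ln(1.458)/0.5545 = 0.680 and power is 74.9%. Moving to the log scale therefore does not rescue the claim unless 1.7 is also geometric.

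**The case against.** The strongest reply is that >95% is not an arithmetical slip. It reproduces from the plan's own inputs on the log scale; a CV is a natural way to state variability for a ratio; and 15.5.2.2 allows a log transformation. On this view the plan is under-specified rather than wrong. The point about origin is fair, and the figure probably was calculated that way. But no section calls 1.7 geometric, the log test is not the primary analysis, and the figures in 15.8 are raw-scale. The stated power does not belong to the stated test.

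A second reply is that the normal model is unrealistic for a ratio. With a CV of 0.6 it puts 4.8% of values below zero, so about 56% of 17-patient samples would contain an impossible value. This stands, and it makes the 83–88% range more credible than 76%. Both ends of that range are still below 95%.

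A third is that the raw and log tests are not directly comparable. In simulation with log-normal ratios at CV 0.6, the raw test rejects in about 7.7% of trials when the arithmetic mean is exactly 1, and it declares an increase in about 8% of trials when the geometric mean is 1. This also stands. Part of the raw test's apparent advantage at a mean of 1.7 reflects a different null and poor size control, which bears on the choice of remedy but does not restore the stated power.

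Finally, the practical stakes are limited. Power is high at the published means, 15.8 does not derive the 20 patients from a power target, and accrual monitoring uses surgical delay only. That is accepted: the fault lies in what is claimed, not in whether the study can be done.

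**Conclusion.** The concern holds. At an arithmetic mean fold-change of 1.7, CV 0.6 and n = 17, the planned raw-scale t-test has 75.7% power under normality and about 83–88% under skewed positive distributions, against more than 95% stated. The result assumes a null of 1 and reads 1.7 as an arithmetic mean, as Sections 8 and 15.5.2.2 imply. If 1.7 was meant as a geometric mean, the figure stands at 95.9% for a log-scale test, but the plan would have to say so and make that test primary. The power statement should be corrected because it supports a primary objective.

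**What to change.** Before any Ki67 results are seen, write the null value and make Sections 5.6, 8, 15.5.2.2 and 15.8 agree, in one of two ways.

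**(a) Keep the raw mean.** State that the null is a mean fold-change of 1. With n = 17, CV 0.6 and two-sided 0.05, give the power at a mean of 1.7 as about 76% under a normal model and 83–88% under skewed models. Give the mean detectable with 95% power as about 2.27 (normal), or 1.83–1.93 (skewed). This is a wording change only, with a less favourable figure. It leaves the size problem of the raw test with skewed ratios.

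**(b) Make the log scale primary.** Specify a one-sample t-test of log(fold-change) against 0, report the geometric mean fold-change with a 95% confidence interval, and keep the Wilcoxon test as a sensitivity analysis. State 96% power for a geometric mean fold-change of 1.7. Add that this is an arithmetic mean of about 1.98 under log-normality, and that power at an arithmetic mean of 1.7 is about 75%. This changes the Section 8 endpoint from an arithmetic to a geometric mean. For log-normal ratios with an arithmetic mean of 1.7, power is nominally lower than with the raw test (75% against 88%), though the two tests address different nulls.

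Neither option needs more patients, samples or data. Either one also removes the open choice of scale after the data are seen, provided the optional transformation in 15.5.2.2 is replaced by a fixed primary analysis.
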